7.5 Efficacy Assessments

During the treatment phase of the study, access to the results of some key efficacy assessments will be restricted from the Investigators and key Sponsor personnel who are involved in the conduct of the study until the study database has been locked. This is specified in a separate document and follows Section II.C (Design Techniques to Avoid Bias) of ICH's Guidance for Industry (E9) Statistical Principles that state that "The double-blind nature of some clinical trials may be partially compromised by apparent treatment induced effects. In such cases, blinding may be improved by blinding investigators and relevant sponsor staff to certain test results...". In the sections below it is specified for which endpoints access will be limited. Specific details of who will have access to each endpoint will be captured in a separate document.

7.5.1 Percentage of Parabasal Cells and Superficial Cells in the Maturation Index of the Vaginal Smear

Vaginal smear samples will be taken from the middle third of the lateral vaginal wall and will be evaluated throughout the study at the central laboratory by a qualified pathologist. The central-laboratory pathologist will perform the cell count associated with the maturation index and determine the proportions of parabasal, intermediate and superficial cells for each sample.

The results of the maturation index at Visit 1 (Screening) will be forwarded to the Investigator for the assessment of eligibility. Date of specimen collection will be entered in the eCRF. If the subject has a vaginal infection (requiring medication) at Visit 1, the infection should be treated, and the vaginal smear must be repeated after resolution of the infection and prior to randomization. The maturation index from the infection-free time point will be used as the baseline value and for assessing eligibility.

Results of the maturation index at Visit 2 (Randomization) will be used as baseline.

During the treatment phase of the study, access to the maturation index results will be restricted from the Investigators (except at Visit 1) and key Sponsor personnel involved in the conduct of the study until the study database has been locked.

7.5.2 Vaginal pH

Vaginal pH will be measured by the Investigator using a pH indicator strip. The pH measurement will be done by pressing the indicator strip against the middle third of the vaginal wall and read while still wet. Two types of pH strips with different ranges will be provided to the study sites. The strips with a pH range from 4 to 7 should be used first. If the measurement is out of the 4 to 7 range, the second pH strip with a range from 2 to 9 should be used. Date of specimen collection and the results will be entered in the eCRF.

The subject will be advised to not use vaginal lubricant and not to have sexual intercourse within 24 hours prior to study visits. If the subject has a vaginal infection (requiring medication) at screening, the pH measurement of the vagina will be repeated after resolution of the infection and prior to the planned randomization. The vaginal pH from the infection-free time-point will be used as the baseline value and for assessing eligibility.

The pH at Visit 2 will be used as baseline.

During the treatment phase of the study, access to the pH results will be restricted from key Sponsor personnel involved in the conduct of the study until the study database has been locked.

7.5.3 Severity of Self-Reported VVA Symptoms

Symptoms of VVA (vaginal dryness, vaginal and/or vulvar irritation/itching, dysuria, vaginal pain associated with sexual activity, and vaginal bleeding associated with sexual activity) will be assessed through the VVA questionnaire (see Appendix 2), to be completed by the subject at every visit. The severity of each symptom will be assessed as none, mild, moderate, or severe by the subject. The study personnel will enter date of questionnaire completion and the subject's responses in the eCRF.

Subjects must have moderate to severe vaginal dryness at Visit 1 in order to be eligible for further screening procedures for the study. Additionally, at Visit 1 and Visit 2, the subject will record which symptom of VVA she finds most bothersome. To be eligible for the study, the subject must report vaginal dryness as her MBS at both Visits 1 and 2.

The severity of vaginal dryness at Visit 2 will be used as baseline and for stratification purposes.

During the treatment phase of the study, access to the VVA symptom data will be restricted from key Sponsor personnel involved in the conduct of the study until the study database has been locked.

7.5.4 Vaginal Health Index [9] (VHI; Appendix 3)

The Investigator will perform an evaluation of the vagina, assessing overall elasticity, fluid secretion, pH, condition of epithelial mucosa and moisture. The severity of each characteristic will be assessed with a five-grade evaluation. Date of evaluation and results of the evaluation will be entered in the eCRF.

If the subject has a vaginal infection (needing medication) at randomization, the visual evaluation of the vagina will be repeated after resolution of the infection and prior to randomization. The assessments from the infection-free time-point will be used as the baseline value.

During the treatment phase of the study, access to the VHI data will be restricted from key Sponsor personnel involved in the conduct of the study until the study database has been locked.

7.5.5 Vulvar Health Index (VuHI; Appendix 4)

Similarly to the VHI, the Investigator will perform a visual examination of the vulva, assessing the labia majora, labia minora, clitoris, introitus appearance and elasticity, color, discomfort and pain, and presence of other findings (eg, petechiae, excoriations, ulcers, etc.). The severity of each characteristic will be assessed as normal/ mild/ moderate/ severe. Date of evaluation and results of the evaluation will be entered in the eCRF.

If the subject has a vaginal infection (needing medication) at randomization, the visual examination of the vulva will be repeated after resolution of the infection and prior to randomization. The assessments from the infection-free time-point will be used as the baseline value.

During the treatment phase of the study, access to the VuHI data will be restricted from key Sponsor personnel involved in the conduct of the study until the study database has been locked.

7.5.6 Vaginal Imaging (Appendix 5)

For patients who agree to participate in the optional vaginal imaging, photographs of the vulva and the vagina will be taken by trained site personnel following the standard procedure described in Appendix 5.

The Sponsor, in cooperation with Canfield Scientific, Inc. (Parsippany, NJ), will provide standardized camera equipment and photography procedures for clinical serial photography of the vulva and the vagina. Photographs will be taken per the vaginal imaging visit schedule, as specified in the Schedule of Time and Events (Table 3.1-1). The photographs will be sent electronically to Canfield as the central repository. Instructions for obtaining and submitting photographs will be provided by Canfield. Date of visit and whether or not the pictures were taken will be entered in the eCRF. After submission, Canfield will assess the quality of the photographs and will

provide a written confirmation of receipt of the photographs and feedback of their quality. If the quality of the photographs is not adequate, a re-shoot should be scheduled as soon as possible but no more than seven days after the original shoot day.

Photographs will be assessed by an Independent Panel Review (IPR) in a blinded fashion and the results of their review will be documented. Canfield will facilitate such review and will collect the data. Access to the Canfield repository where photographs and results of the IPR assessment will be stored, will be restricted from the Sponsor and from the Investigators.

During the treatment phase, access to the photographs and results of the IPR assessment will be restricted from the Investigators and key Sponsor personnel involved in the conduct of the study until the study database has been locked.

Procedures to be followed by the IPR will be described in a separate document (IPR charter).

7.5.7 Female Sexual Function Index (FSFI; Appendix 6)

Subjects will complete the Female Sexual Function Index (FSFI) [10] questionnaire and study personnel will enter the date of completion and the responses in the eCRF.

7.5.8 Urinary Distress Inventory (UDI-6; Appendix 7)

The presence or absence of urinary symptoms (urgency, frequency, incontinence, retention, and pain or discomfort) will be assessed using the Urinary Distress Inventory (UDI-6) [11]. The subject will complete the questionnaire and the study personnel will enter the date of completion and the responses in the eCRF.

7.5.9 Efficacy laboratory Tests

The following hormones will be measured in serum:

- Estradiol (E₂)
- Follicle-stimulating Hormone (FSH)

FSH levels may also be measured at Screening (Visit 1) only to confirm menopausal status, Inclusion Criterion #3 b. Is ≥ 45 years old; she does not remember the date of her last spontaneous menstrual bleeding and has follicle-stimulating hormone (FSH) levels >40 IU/L **OR** c. Has had a hysterectomy **WITHOUT** oophorectomy and serum FSH levels >40 IU/L, as needed.

- Luteinizing hormone (LH)
- Sex hormone binding globulin (SHBG)
- Free testosterone
- Total testosterone

The serum hormones will be analyzed by the central laboratory. The date of specimen collection will be entered in the eCRF.

During the treatment phase of the study, access to results of hormone levels will be restricted from the Investigators (except FSH at Visit 1) and key Sponsor personnel involved in the conduct of the study until the study database has been locked.

7.5.10 Markers of Bone Metabolism

Markers of bone metabolism will be measured during the Treatment Period of the study to assess the early effect of ospemifene on bone metabolism. Blood and urine samples to measure markers of bone metabolism will be obtained and sent to a central laboratory for analysis. Date of specimen collection will be entered in the eCRF. Markers of bone metabolism will include the following:

7.5.10.1 Markers of Bone Resorption:

- Serum N-telopeptide of type 1 collagen (NTX)
- Serum C-terminal telopeptide of type 1 collagen (CTX)
- Serum Bone sialoprotein (BSP)
- Urinary Deoxypyridinoline (DPD)
- Serum tartrate-resistant acid phosphatase 5b (TRACP-5b)

7.5.10.2 Markers of Bone Formation:

- Serum total alkaline phosphatase
- Serum bone specific alkaline phosphatase (BSAP)
- Serum aminoterminal propeptide of type 1 collagen (P1NP)
- Serum Osteocalcin

During the treatment phase of the study, access to results of markers of bone metabolism will be restricted from key Sponsor personnel involved in the conduct of the study until the study database has been locked.

7.5.11 Special Considerations Concerning Efficacy Variables

7.5.11.1 Urine Dip-Stick Test

At Visits 1 and 2, a urine dip-stick test will be performed and read at the site to screen for a urinary tract infection (UTI). If the result indicates a UTI is present, the UTI must be treated to resolution before any efficacy assessments are completed.

Any UTI diagnosed after the time of Informed Consent will be recorded as a Medical History or AE, and should be treated according to the clinical judgment of the Investigator. Any concomitant treatments for UTI should be recorded in the eCRF.

7.5.11.2 Vaginal Infection

At all visits the sequence of procedures should follow Section 8. However, if a vaginal infection requiring medication (e.g. candida vaginitis) is identified at Visit 1 (screening) or at Visit 2 prior to randomization, the infection must be treated to resolution. After the vaginal infection is treated, 2 weeks (14 days) should be allowed to restore the local environment before continuing the screening or randomization procedures. The time necessary to treat the infection will not count against the 4-week duration of the screening period. If a vaginal infection is identified please follow these procedures:

1. If the vaginal infection is discovered during the gynecological examination (Visit 1 or Visit 2), the vaginal pH, the vaginal smear for maturation index, and the sample for cervical PAP, along with the rest of the remaining assessments for that visit, should not be conducted until the resolution of the infection is confirmed. The VVA questionnaire needs to be repeated as it should have been conducted before the gynecological examination.
2. If the infection is identified based on the results of cervical pap or vaginal smear for maturation index obtained at Visit 1, the infection should be treated until resolution. The patient should then return for an Unscheduled Visit (prior to Visit 2) for a repeat of the VVA questionnaire, gynecological examination, vaginal pH, vaginal smear (maturation index), and cervical pap, to confirm eligibility. If eligible based on these results the subject may continue to Visit 2.
3. If the infection takes longer than 30 days to treat, safety laboratory tests (hematology and chemistry) should be repeated at an Unscheduled Visit at the infection-free timepoint to confirm eligibility. If eligible based on these results the subject may continue to Visit 2 if the infection was diagnosed prior to Visit 2 or continue with the outstanding procedures from Visit 2 if the infection was diagnosed at Visit 2.
4. In the situations described in items 2 and 3 above, results of tests repeated between Visit 1 and Visit 2, at the infection-free timepoint, will be used to confirm eligibility (Visit 1) as well as baseline values (Visit 2) and do not need to be repeated again at Visit 2. The TVU, endometrial biopsy, and ECG do not need to be repeated even if they were assessed prior to the discovery of the infection.

Any vaginal infection diagnosed after the time of the informed consent will be recorded as an AE and should be treated according to the clinical judgment of the Investigator. Any medication used as treatment for a vaginal infection should be recorded in the Concomitant Medication eCRF.

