| Concomitant Therapy | | | X | X | X | X |
| Adverse Events | X ^j | X | X | X | X | X |

| Evaluation | Screening | Randomization | Treatment | | | FU ^q |
|--|--|----------------|-----------|------|----------------|-----------------|
| | V1 | V2 | V3 | V4 | V5 | TC |
| | Within 4 Weeks Prior to Day 1 ^a | Day 1 | Wk 4 | Wk 8 | Wk 12/ ET | Wk 14 |
| Cervical PAP Smear | X ^o | | | | | |
| Vaginal pH | X ^o | X ^p | X | X | X | |
| Vaginal Smear/ Maturation Index | X ^o | X ^p | X | X | X | |
| Vaginal Health Index (VHI) | | X | X | X | X | |
| Vulvar Health Index (VuHI) | | X | X | X | X | |
| Vulvo-Vaginal Imaging ^k | | X | | | X | |
| Endometrial Thickness (TVU) | X | | | | X | |
| Endometrial Histology (Biopsy) | X | | | | X ⁿ | |
| Mammogram | X ^l | | | | | |
| Dispense eDiary/Return eDiary | | X | | | X | |
| eDiary Compliance | | | X | X | X | |
| Assessment of symptoms of VVA | X ^o | X ^p | X | X | X | |
| Dispense Study Medication | | X | X | X | | |
| Dispense Lubricant | | X | X | X | | |
| Study Medication Compliance ^m | | | X | X | X | |
| Reinforce Compliance with Study Medication | | X | X | X | | |
| Study Medication Return | | | X | X | X | |
| Female Sexual Function Index (FSFI) | | X | X | X | X | |

| Evaluation | Screening | Randomization | Treatment | | | FU ^q |
|------------------------------------|--|---------------|-----------|------|--------------|-----------------|
| | V1 | V2 | V3 | V4 | V5 | TC |
| | Within 4 Weeks Prior to Day 1 ^a | Day 1 | Wk 4 | Wk 8 | Wk 12/ ET | Wk 14 |
| Urinary Distress Inventory (UDI-6) | | X | X | X | X | |

ET = Early termination; **FU** = Follow-up; **TC** = Telephone call.

- a Enough time between Visit 1 and Visit 2 should be allowed to receive the results of tests conducted as part of Visit 1, therefore, Visit 2 should not take place earlier than 1 week after Visit 1.
- b Subject ID number will be assigned through the interactive web or voice response system (IxRS).
- c Medical history should be captured for the 2 years prior to screening, except for any history of cancer which should be captured regardless of the time.

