- l May be omitted in subjects with a normal mammogram within 9 months prior to screening for which the results are available.
- m To be assessed based on pill count. When there is a discrepancy between the pill count and the subject-reported compliance, the subject-reported compliance should be used.
- n Do not perform if discontinuation (early termination) occurs PRIOR to VISIT 5 (Week 12).
- o Repeat after cure of infection at V1.

- p Repeat after cure of infection at V2.
- q Follow-up call should occur ON Day 14 after last dose. In case subject does not respond, three follow-up attempts should be made.

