6.3 Study Day and Analysis Windows

Day 1 is the initial dose date for subjects. Previous day to Day 1 is expressed as Day -1, and days before Day -1 in Screening Period are expressed as Day -2, Day -3, ... , etc.

Allowance window for each of the scheduled visits is shown in Table 1.

Allowance window for diary data is shown in Table 2.

If more than one visit occurs during a visit window, the one closest to the target day will be assigned to the visit. If two visits are equidistant from the target day, the latter visit will be assigned to the visit for post-baseline values.

If a subject discontinues from the study, the data obtained at early termination visit will be treated as one visit data based on the allowance windows.

Table 1 Definition of Visit Window

Scheduled Visit	Target Day	Window (Days)
Visit 1	Day -28	≤ Day -1
Visit 2 (Day 1)	Day 1(Randomization)	Day 1
Visit 3 (Week 4)	Day 29	Day 16 to Day 43
Visit 4 (Week 8)	Day 57	Day 44 to Day 71
Visit 5 (Week 12)	Day 85	Day 72 to Day 99
Early termination	Last dosing date	+ 14

Table 2 Definition of Diary Data Window

Week	Daily Data	Weekly Data (Target Day)
Week 1	Day 1 to Day 7	Day 4 to Day 10 (Day 7)
Week 2	Day 8 to Day 14	Day 11 to Day 17 (Day 14)
Week 3	Day 15 to Day 21	Day 18 to Day 24 (Day 21)
Week 4	Day 22 to Day 28	Day 25 to Day 31 (Day 28)
Week 5	Day 29 to Day 35	Day 32 to Day 38 (Day 35)

Week	Daily Data	Weekly Data (Target Day)
Week 6	Day 36 to Day 42	Day 39 to Day 45 (Day 42)
Week 7	Day 43 to Day 49	Day 46 to Day 52 (Day 49)
Week 8	Day 50 to Day 56	Day 53 to Day 59 (Day 56)
Week 9	Day 57 to Day 63	Day 60 to Day 66 (Day 63)
Week 10	Day 64 to Day 70	Day 67 to Day 73 (Day 70)
Week 11	Day 71 to Day 77	Day 74 to Day 80 (Day 77)
Week 12	Day 78 to Day 84	Day 81 to Day 87 (Day 84)

Assessments that occur more than 14 days after the last dose of study medication will be excluded from the above visit windows.

The baseline is defined as the last value that is observed prior to the first dose of study medication. For a variable that is planned to be observed at screening and randomization, the data at randomization will be used as baseline. For such variable, if the data at randomization is missing for a subject, the data observed at screening will be used as baseline.

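### FSFI and UDI-6 are not listed for repeat after a vaginal infection found at the Visit 2 examination, so their baselines come from the infected visit

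*Protocol*

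**What the plan says.** **Order of procedures.** Protocol 7.5.11.2 opens with "At all visits the sequence of procedures should follow Section 8". Section 8.2 lists the Visit 2 steps with VVA symptoms, FSFI and UDI-6 one after another, then vital signs and the physical, breast and gynecological examinations. Randomization through the IxRS comes near the end.

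**Infection found at the examination.** Item 1 of 7.5.11.2 postpones pH, smear, PAP sample and the other assessments not yet done. For what has already been completed it names one questionnaire: "The VVA questionnaire needs to be repeated as it should have been conducted before the gynecological examination". Item 3 covers infections that take more than 30 days to treat; there the woman is to "continue with the outstanding procedures from Visit 2 if the infection was diagnosed at Visit 2".

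**Schedule.** Footnote p of Table 3.1-1 reads "Repeat after cure of infection at V2". At Visit 2 it is attached to the gynecological examination, safety laboratory tests, vaginal pH, vaginal smear and VVA symptoms. The other two questionnaires appear without it: "Female Sexual Function Index (FSFI) | | X | X | X | X" and "Urinary Distress Inventory (UDI-6) | | X | X | X | X". SAP Appendix 1 shows the same.

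**Baseline.** SAP 6.3: "The baseline is defined as the last value that is observed prior to the first dose of study medication". Neither the FSFI nor the UDI-6 is collected at Visit 1.

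**Urinary tract infection, for contrast.** Protocol 7.5.11.1: "the UTI must be treated to resolution before any efficacy assessments are completed".

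**The concern.** Item 1 repeats the VVA questionnaire because it was filled in before the infection came to light. The FSFI and UDI-6 were filled in at the same point, so the stated reason covers them too, yet a site that follows the text exactly will not repeat them. Sections 7.5.1, 7.5.2, 7.5.4 and 7.5.5 say that an infection-free value serves as baseline for maturation index, pH, VHI and VuHI. Sections 7.5.7 (FSFI) and 7.5.8 (UDI-6) have no such sentence. This looks like an oversight rather than a choice.

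The two instruments make up secondary Objective 2. SAP 9.2.8 and 9.2.9 analyze both as change from baseline by ANCOVA with the baseline score as covariate. UDI-6 item 6 asks about lower abdominal or genital pain or discomfort, and FSFI items 17 to 19 score pain with penetration, so a symptomatic vaginal infection can plausibly worsen both. Recovery from the infection would then appear as improvement on study in the affected women.

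Their baselines would also be older than the others by at least the 14-day wait plus the treatment time. One woman could have an infection-free VVA score for pain with sexual activity next to an FSFI pain score from the infected visit. Sites that repeat all three questionnaires on their own initiative would produce baselines of a different kind from sites that follow the text.

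**Working it through.** **1. Which women are affected**

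| Where the infection is found | FSFI and UDI-6 already done? | Baseline under the text |
|---|---|---|
| Visit 1 examination, or Visit 1 PAP or smear result | No, first given at Visit 2 | After cure |
| Visit 2 dipstick (UTI) | No, the dipstick is read first | After resolution |
| Visit 2 gynecological examination (vaginal infection) | Yes | Infected visit |

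Only the last row is a problem. In that row the VVA questionnaire, pH and smear are repeated or deferred until after cure, and VHI and VuHI follow the examination in 8.2 and are deferred with it.

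**2. Is the treatment comparison biased?**

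The examination precedes the IxRS call in 8.2, and item 1 halts the visit until cure. Infection status at the questionnaire is therefore fixed before allocation and independent of arm. The expected baseline shift is the same in both arms, and the expected between-arm difference is unchanged.

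**3. The plan's own figure**

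The documents contain no figure for this point. Their one sample-size claim is at least 90% power with 300 per arm. For dryness (effect size 0.27) power is Φ(0.27 × √150 − 1.96) = Φ(1.347) = 0.911, and the other three co-primary endpoints exceed 0.999, so the claim reproduces. It does not concern FSFI or UDI-6; only the total of 600 is used below.

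**4. Size in score points (assumed inputs)**

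Assume 2% to 6% of women have an infection found at Visit 2: 600 × 0.02 = 12 to 600 × 0.06 = 36 women.

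- UDI-6 total (six items scored 0 to 4, range 0 to 24). Assume infection worsens it by 1 to 4 points. Inflation of mean change in each arm = rate × shift: 0.02 × 1 = 0.02 to 0.06 × 4 = 0.24 points.
- FSFI pain domain (three items, factor 0.4, range 0 to 6). Assume 1 to 2 points per item: 0.4 × 3 × 1 = 1.2 to 0.4 × 3 × 2 = 2.4 points in an affected woman. Per-arm mean: 0.02 × 1.2 = 0.024 to 0.06 × 2.4 = 0.144 points.

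**5. Size in SD units (wider assumed range)**

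Let a share f of women have a baseline worsened by s SD, and let the true baseline correlate 0.6 with follow-up (assumed).

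- Within-arm inflation = f × s: 0.01 × 0.3 = 0.003 SD to 0.10 × 1.0 = 0.10 SD.
- ANCOVA standard error ratio = √[(1 − 0.36/v) / 0.64], with v = 1 + f(1 − f)s².

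| f | s (SD) | v | SE ratio, formula | SE ratio, simulated |
|---|---|---|---|---|
| 0.02 | 1.0 | 1.0196 | 1.005 | 1.007 |
| 0.05 | 1.0 | 1.0475 | 1.013 | 1.008 |
| 0.10 | 1.0 | 1.0900 | 1.023 | 1.016 |

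The simulation used 300 per arm, a true difference of 0.2 SD and 1,500 replicates per setting. In all 12 settings run (f of 0.01, 0.02, 0.05 and 0.10; s of 0.3, 0.5 and 1.0) the estimated difference agreed to three decimals with that from the uncontaminated baseline. The gap between the last two columns is within simulation error.

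**6. What a repeat would recover**

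The FSFI looks back 4 weeks (28 days), and 7.5.11.2 allows 14 days after treatment before procedures resume. A repeat on day 14 still covers 28 − 14 = 14 days that may be infected or under treatment, which is 14/28 = half the window. The UDI-6 in Appendix 7 states no recall period.

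**The case against.** The best reply is that this hardly matters. Visit 1 already looks for infection by examination, PAP and smear, with treatment and retest, so only new or missed infections reach the Visit 2 examination. UTI, the obvious confounder of a urinary questionnaire, is dealt with before any questionnaire is given. All four co-primary endpoints have infection-free baselines, and the planned inference on FSFI and UDI-6 is between arms. All of this stands.

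The assumed shifts may also be generous. If item 6 alone moves on the UDI-6, a 4-point shift means every affected woman going from symptom absent to greatly bothered. On the FSFI, a woman who did not attempt intercourse scores 0 on all three pain items whatever her infection status.

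Recall is a weaker objection. The VVA questionnaire in Appendix 2 also looks back about a month, and the protocol repeats it nonetheless.

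A reader might infer more than the documents support:

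- *That the estimated drug effect is biased.* It is not in expectation, because infection status is settled before randomization.
- *That the VVA questionnaire is the only thing repeated.* That is true among the questionnaires only; footnote p covers four other rows.
- *That these are the only efficacy baselines left at the infected visit.* Section 8.2 also collects the urine sample for bone markers before the examination, and the bone-marker row has no footnote p. Nothing in the documents suggests that a vaginal infection alters that marker, so it does not add to the concern.

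**Conclusion.** The gap holds and neither document closes it: followed exactly, the text gives FSFI and UDI-6 baselines from the infected visit to women whose vaginal infection is found at the Visit 2 examination. The consequence is small. It consists of added noise and overstated within-arm change on two secondary endpoints, in an unknown and probably small number of women. Even at 10% affected and a full SD of worsening, the ANCOVA standard error rises by about 2%.

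That there is no expected bias follows from the order of steps in 8.2. The magnitudes rest on assumed infection rates, assumed shifts and an assumed correlation, none of which the documents supply. This is an inexpensive correction worth making for consistency, not a threat to the trial's conclusions.

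**What to change.** - In 7.5.11.2 item 1, say that the VVA questionnaire, the FSFI and the UDI-6 all need to be repeated.
- Add superscript p to the Visit 2 FSFI and UDI-6 cells in Table 3.1-1 and in SAP Appendix 1.
- In 7.5.7 and 7.5.8, state that the post-cure values are the baseline. The SAP 6.3 definition needs no change, since a repeated score would be the last one before the first dose.
- In 7.5.7, acknowledge that part of the FSFI recall period may still fall before or during treatment of the infection, and say how that is handled. The repeat reduces the contamination but should not be described as a fully infection-free FSFI.

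The cost is a few words and two superscripts in each schedule, plus two short questionnaires repeated by the affected women at a visit they attend anyway for the deferred procedures.
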